9.8.1. Samples for Immunogenicity Testing

Blood samples for immunogenicity testing will be collected to determine antibody production against insulin lispro as specified in the Schedule of Activities (Section 2 and Appendix 8).

Immunogenicity will be assessed by a validated radio ligand-binding assay (RBA) to detect anti-insulin lispro antibodies in the presence of lispro. Instead of quantitating the level of anti-insulin lispro antibodies by titer, the RBA reports a semiquantitative percent-binding for each positive sample. Additionally, positive samples will be characterized for cross-reactive binding to native insulin.

Clinical and reliable on-market data indicate that the immunogenic potential of insulin lispro is comparable to other marketed insulins such as regular human insulin (Fineberg et al. 1996) and, when present, anti-insulin antibodies do not appear to be clinically consequential (Fineberg et al. 2003). Therefore, rather than relying on an *in vitro* neutralization assay, well established *in vivo* measures of insulin lispro efficacy (that is, insulin dose, HbA1c) will be utilized to directly monitor for any potential neutralizing effect of anti-lispro antibodies.

Patients who complete the 4-week safety follow-up visit and have treatment-emergent anti-insulin lispro antibodies that have not returned to prespecified baseline range (Visit 2) will be asked to participate in follow-up to monitor antibody levels. Instructions for this follow-up assessment are provided in Appendix 8.

Samples will be retained for a maximum of 15 years after the last patient visit for the study, or for a shorter period if regulations and ERBs impose shorter time limits, at a facility selected by Lilly or its designee. The duration allows the sponsor to respond to future regulatory requests related to LY900014.

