Unless otherwise noted, all tests of treatment effects will be conducted at a 2-sided alpha level of 0.05, and CIs will be calculated at 95%, 2-sided. All tests of interactions between treatment groups and other factors will be conducted at a 2-sided alpha level of 0.10.

The definitions of baseline and postbaseline for the efficacy and safety analyses depend on which analysis period is being used. The following analysis periods will be used:

- Lead-in Period – Visits 2-8
- 26-Week Treatment Period – from randomization to Week 26 prior to discontinuation of IP and from randomization to Week 26 (including all data regardless of IP use) – all treatment groups
- 26-Week Treatment Period and Safety Follow-Up Visit – from randomization to Visit 801 (including all data regardless of IP) – LY900014+20 treatment group excluding patients from Japan
- 52-Week Treatment Period - from randomization to Week 52 prior to discontinuation of IP and from randomization to Week 52 (including all data regardless of IP use) – double-blind treatment groups
- 52-Week Treatment Period and Safety Follow-Up Visit – from randomization to Visit 801 (including all data regardless of IP use) – double-blind treatment groups.

Patients randomly assigned to the LY900014+20 treatment group in Japan will remain in the study until Week 52 and subsequently will have the Safety Follow-Up Visit only after Week 52 for patients who complete the study.

The data on IP is defined based on the following rules:

- for data only measured at an office visit
 - MMTT postbaseline data will be considered as data on IP if the MMTT performance date is on or prior to the last IP dose date
 - Other postbaseline data (for example, vital signs, laboratory tests, and questionnaires) will be considered as data on IP if the measurement date is on or prior to the cutoff date defined as 14 days after the last IP dose date
- for data collected as running records with an exact date stamp such as adverse events (AEs) and diary entries where the dates of the measures were not tied with the date of an office visit, postbaseline data with dates \leq (last study drug dose date +1) will be considered as data on IP.

Table 6.2 describes the rules for determining the patient population, baseline and postbaseline observations for the different analysis periods.

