Both actual and change from baseline (Visit 2) for the anti-insulin lispro antibody level in percent binding will be summarized by scheduled visit prespecified in the protocol for patients with positive TEADA response during the treatment period of 0 to 26 weeks. The repeated measurement from Visit 2 to Visit 18 will be analyzed by an MMRM model with treatment, baseline value of the response variable, visit, and visit by treatment interaction as fixed factors and patient as the random factor. The ANCOVA model using treatment and baseline value as covariates will be used for the analysis of maximum percent binding during the treatment period of 0 to 26 weeks. A similar summary of antibody level in percent binding during the analysis period of Visit 2 to Visit 801 will be generated separately for the 2 double-blind treatment groups and the open-label treatment group.

A listing of anti-insulin lispro antibody at each visit will be provided. The listing will include anti-insulin lispro antibody status (detected/not detected), anti-insulin lispro antibody percent binding, TEADA status (positive/negative), insulin cross-reactivity status, insulin cross-reactivity percent binding for the safety population.

Subgroup analysis for the following selected efficacy and safety variables will be performed by the TEADA status during the treatment period of 0 to 26 weeks:

- Use data prior to discontinuation of IP:
 - HbA1c and change from baseline in HbA1c
 - 1-hour and 2-hour PPG excursions
 - basal, prandial, and total insulin dose
 - event rate (per patient per year) of overall hypoglycemic events
- Use all data regardless of IP use:
 - treatment-emergent injection site reaction and hypersensitivity reaction

The analyses for HbA1c and change from baseline in HbA1c will be performed using an MMRM model for the primary analysis and the HbA1c data prior to discontinuation of IP. The model will include additional fixed terms of subgroup, subgroup by treatment interaction, subgroup by visit interaction, and 3-way interaction of treatment, subgroup, and visit.

The PPG excursions will be analyzed by the ANCOVA model same as the model specified in Section 6.11.2 using the efficacy estimand. The model will include additional terms of subgroup, subgroup by treatment interaction, subgroup by visit interaction, and 3-way interaction of treatment, subgroup, and visit.

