The subgroup analysis for insulin dose will use the MMRM model specified in Section 6.11.5 using the efficacy estimand. The model will include additional fixed terms of subgroup, subgroup by treatment interaction, subgroup by visit interaction, and 3-way interaction of treatment, subgroup and visit.

The treatment emergent injection site reaction and hypersensitivity reaction will be analyzed by a logistic regression model including terms of treatment, subgroup, and treatment by subgroup interaction. All data regardless of IP use will be used for this analysis.

The negative binomial regression model specified in Table 6.6 with additional terms of subgroup, treatment by subgroup interaction will be used for the subgroup analysis of overall hypoglycemia event rate while on IP.

The interaction effects (3-way for MMRM and 2-way for ANCOVA/logistic regression model/negative binomial regression model) will be evaluated using a significance level of 0.10, unadjusted. If the interaction effect is significant ($p < 0.10$), separate analyses without the terms related to the subgroup will be performed for each subpopulation.

The above subgroup analyses may be repeated for the 2 double-blind treatment groups using the subgroup defined by TEADA status during the analysis period of Visit 2 to Visit 801.

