6.13. Subgroup Analyses

6.13.1. Subgroup Analyses for HbA1c

The following subgroups will be analyzed for HbA1c if there are sufficient numbers of patients per group (for example, at least 10% in each group) using data collected from all randomized patients prior to discontinuation of IP through Week 26:

- age (<40, ≥40 years)
- hemoglobin A1c stratum (≤7.5% vs. >7.5%)
- patient's personal CGM/FGM use during the study (Yes vs. No)
- sex (male vs. female)
- body mass index (<25 vs. ≥25, and <30 vs. ≥30 kg/m²)
- duration of diabetes (using the median as the cut-off)
- race
- ethnicity
- country
- region (Europe, North America, Eastern Asia [Japan, Taiwan, Korea], and Other [India, Mexico, Argentina, Australia, New Zealand])
- baseline 1-hour PPG excursion (≤ baseline median, > baseline median)
- baseline 1-hour PPG (PPG ≤180 mg/dl, >180 mg/dl)
- baseline 2-hour PPG excursion (≤ baseline median, > baseline median)
- baseline 2-hour PPG (PPG ≤180 mg/dl, >180 mg/dl)
- type of basal insulin during the lead-in period (glargine U-100 vs. degludec U-100)
- prandial insulin dosing plan (carbohydrate counting or pattern adjustment)

Analyses for HbA1c and change from baseline in HbA1c will be performed using an MMRM model that includes the same fixed effects given for the primary analysis model plus factors of subgroup, 2-way interaction of subgroup and treatment, 2-way interaction of subgroup and visit, and 3-way interaction of treatment, visit and subgroup. The interaction of subgroup and treatment at the primary endpoint (Week 26) will be evaluated to assess the treatment by subgroup interaction. When analyzing HbA1c stratum as a subgroup the baseline HbA1c will not be included as a covariate to avoid confounding. The subgroup interaction effect will be evaluated using a significance level of 0.10, unadjusted.

Additional subgroup analyses may also be performed.

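### SAP 6.12.7.1 judges whether anti-lispro antibody status modifies the treatment effect on HbA1c and insulin dose by a 3-way term that is zero when the modification is the same at every visit

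*SAP*

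**What the plan says.** SAP 6.12.7.1 plans subgroup analyses by TEADA status over Weeks 0 to 26. For HbA1c, the primary MMRM gains a TEADA main effect plus "subgroup by treatment interaction, subgroup by visit interaction, and 3-way interaction of treatment, subgroup, and visit". Insulin dose gets the same extra terms in the MMRM of SAP 6.11.5.

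The section then fixes which term is judged: "The interaction effects (3-way for MMRM and 2-way for ANCOVA/logistic regression", with negative binomial models also on the 2-way side. These effects "will be evaluated using a significance level of 0.10, unadjusted". SAP 6.1 gives the same level and makes it 2-sided: "All tests of interactions between treatment groups and other factors will be conducted at a 2-sided alpha level of 0.10". If the test is significant, "separate analyses without the terms related to the subgroup will be performed for each subpopulation". HbA1c and insulin dose therefore fall under the 3-way rule. PPG excursions, injection site and hypersensitivity reactions, and overall hypoglycemia rate fall under the 2-way rule.

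For the other HbA1c subgroups, SAP 6.13.1 adds the same set of terms to the same MMRM but judges a different one: "The interaction of subgroup and treatment at the primary endpoint (Week 26) will be evaluated to assess the treatment by subgroup interaction".

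Protocol 9.8.1 explains why HbA1c and dose matter here. Instead of an in vitro neutralization assay, in vivo measures such as these "will be utilized to directly monitor for any potential neutralizing effect of anti-lispro antibodies".

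**The concern.** Effect modification by antibody status means that the treatment difference is not the same in TEADA-positive and TEADA-negative patients. The 3-way term does not measure that. It measures whether the gap between the two treatment differences varies from visit to visit. A gap that is present by Week 4 and stays the same to Week 26 leaves the 3-way term at zero, even if the gap is large.

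The two outcomes under this rule are the two that the protocol cites for monitoring neutralization. A nonsignificant 3-way p-value also switches off the separate analyses by TEADA status, and could be reported as showing no influence of antibodies. The SAP gives no reason for treating antibody status differently from the subgroups in 6.13.1.

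**Working it through.** **1. The plan's own figures.** SAP 5.2 gives SD 1.1%, 371 completers per double-blind arm, 15% dropout and 4:4:3 allocation. SE = 1.1 × √(2/371) = 0.0808. Power is Φ(0.4/0.0808 − 1.96) = Φ(2.99) = 99.9% (stated: at least 99%) and Φ(0.3/0.0808 − 1.96) = Φ(1.75) = 96.0% (stated: 95%). 371/0.85 = 436.5, against 436 in protocol 10.1. For the open-label arm, 0.85 × 327 = 278 completers. These inputs are used below. The documents state no power for the TEADA interaction.

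**2. What each test asks.** Let d_k be the treatment effect in TEADA-positive patients minus that in TEADA-negative patients at visit k. SAP Table 6.2 uses Visits 11, 13, 15 and 18 (Weeks 4, 8, 12 and 26) for both HbA1c and insulin dose.

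- 3-way null: d_11 = d_13 = d_15 = d_18, for each of two treatment contrasts (6 df).
- Week 26 null: d_18 = 0, for each of two treatment contrasts (2 df).

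If every d_k equals d, each contrast d_k − d_18 is 0 and so is the noncentrality. The 3-way test then rejects at its alpha of 10%. This needs no assumption about SD, TEADA share or correlation, and it applies to insulin dose as well as HbA1c.

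**3. Constant modification of 0.3% HbA1c in both LY900014 arms.** Assumed, and not in the documents: TEADA share p of 10, 30 or 50%, equal in all arms; compound symmetry with correlation ρ = 0.7. With the same modification in both LY900014 arms, the Week 26 noncentrality is

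λ26 = 0.3² / {[1.1²/(p(1−p))] × [1/371 + 1/(371+278)]}.

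For p = 0.3: 0.09 / (5.762 × 0.004236) = 3.69. The 10% critical values are 4.61 (2 df) and 10.64 (6 df).

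**4. Growing modification (25/60/85/100% of 0.3%).** Under compound symmetry, λ(3-way) = λ26 × S/(1−ρ), where S is the sum of squared deviations of the profile from its mean. The mean is 0.675 and S = 0.1806 + 0.0056 + 0.0306 + 0.1056 = 0.3225. At ρ = 0.7 the factor is 1.075.

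| TEADA share | λ26 | Week 26 test | 3-way, constant | λ(3-way), ramp | 3-way, ramp |
|---|---|---|---|---|---|
| 10% | 1.58 | 29% | 10% | 1.70 | 22% |
| 30% | 3.69 | 51% | 10% | 3.96 | 39% |
| 50% | 4.39 | 58% | 10% | 4.72 | 44% |

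**5. Sensitivity.**

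- For a constant 0.5%, the Week 26 test has 58/89/94% and the 3-way test 10%.
- Simulation of a constant 1.0% gives 9.6 to 10.4% for the 3-way test, against 99 to 100% at Week 26.
- For linear growth to 0.5% at Week 26, with compound symmetry at 0.5 or 0.7 or AR(1) at 0.7, the 3-way test has 31 to 93%, against 58 to 94%.
- The ordering for a growing effect depends on the correlation. At ρ = 0.8 the ramp factor becomes 0.3225/0.2 = 1.61. At a 30% share λ is then 5.95 and power 53%, slightly above the 51% of the Week 26 test. The constant case is unaffected by ρ.

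**The case against.** **The gate is narrow.** It controls only the extra separate analyses. The model with all TEADA terms is fitted regardless, and SAP 6.1 promises LS means, treatment differences and 95% CIs from the analysis models. This stands. A reader might infer that the SAP has no analysis able to show a stable antibody effect; it does, since the Week 26 estimate comes from a model already planned. But SAP 6.1 does not say that results will be shown by TEADA status, and no decision rests on the 2-way term.

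**A constant effect is not the likeliest shape.** HbA1c integrates over months, prandial dose is titrated over Weeks 0 to 12, and antibodies may appear late. This also stands. A growing modification is partly detected, so it would be wrong to say that modification in general goes undetected.

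**Neutralization common to all arms.** All three arms receive lispro, so a reader might infer that leaving out a TEADA-positive versus TEADA-negative contrast is a further defect. The documents do not support that. Objective 18 is a between-arm comparison of antibody incidence and is tertiary/exploratory. TEADA is a post-randomization status, and insulin is titrated to glucose targets, so such a contrast is not a randomized comparison and could not be read as a test of neutralization. Protocol Appendix 8 and SAP 6.12.7.2 also address loss of efficacy, though only descriptively and only in patients in antibody follow-up.

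**PPG visit terms.** "The PPG excursions will be analyzed by the ANCOVA model same as the model specified in Section 6.11.2 using the efficacy estimand", and the section then adds visit interactions although the MMTT has one postbaseline visit. This is clerical: the ANCOVA is judged by the 2-way term in any case, and the extra terms drop out.

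**Conclusion.** The rule is wrong as written for HbA1c and insulin dose. For a modification of equal size at all visits, the named test rejects 10% of the time whatever the effect; that follows from algebra alone. The Week 26 test in SAP 6.13.1 would reject 29/51/58% of the time for a 0.3% HbA1c modification at TEADA shares of 10/30/50%. For a growing modification, the 3-way test was the weaker in every scenario at correlations of 0.5 and 0.7, but not at 0.8.

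The percentages rest on an assumed TEADA share, correlation and effect size. They use the planning SD of 1.1%; a smaller baseline-adjusted SD would raise the Week 26 power and leave the 10% unchanged. No power is given for insulin dose because the documents give no SD for it.

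A reader might conclude that the trial cannot address neutralization at all. That goes too far: the fault lies in which interaction p-value is named and what depends on it. The analysis is exploratory, and neither the primary nor the multiplicity adjusted objectives are touched.

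**What to change.** In SAP 6.12.7.1, replace the 3-way criterion for MMRM outcomes with the treatment-by-TEADA interaction at Week 26, as in 6.13.1, and make the separate analyses depend on that test. From the same model, report the Week 26 treatment differences within TEADA-positive and TEADA-negative patients with 95% CIs for HbA1c and insulin dose, whatever the interaction p-value.

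Optional: show the TEADA-positive minus TEADA-negative difference descriptively, labelled as a non-randomized comparison. As an editorial clean-up, delete the visit terms from the PPG ANCOVA.

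The cost is one changed criterion, one added sentence and a few contrasts from models already planned. No new data or models are needed.

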6.12.7.2. Anti-Insulin Lispro Antibody Return to Baseline

Any patient who develops a TEADA response at any time during the treatment period (0 to 52 weeks for double-blind treatment groups and 0 to 26 weeks for open-label treatment group) that has not returned to baseline at Visit 801 should undergo follow-up for antibodies to insulin lispro for a maximum of 6 months after Visit 801 or until anti-insulin lispro antibodies return to baseline range, whichever occurs sooner. The analyses for return to baseline will only include patients meeting this antibody follow-up entry criteria. Return to baseline (RBL) is defined as

- not detected postbaseline anti-insulin lispro antibody level at or after Visit 801 for patients with not detected status at baseline, or
- the detected postbaseline anti-insulin lispro antibody level (percent binding) at or after Visit 801 is less than 157% of the baseline value for patients with detected status at baseline.

Reasons for discontinuation from the antibody follow-up at Visits 802 and 803 will be summarized by the randomized treatment groups. No treatment comparison will be conducted.

Duration of exposure to IP will be summarized by treatment groups. Only descriptive statistics: n, mean, SD, median, minimum, maximum, and sum (that is, total patient-years of exposure), will be provided.

The number and percentage of patients whose anti-insulin lispro antibody levels meet the RBL criteria will be summarized by visit (Visit 802, and 803).

For the patients participating in the insulin antibody follow up, a summary of HbA1c, the insulin dose (prandial, basal, and total daily insulin dose), vital signs, body weight, AEs and concomitant medications reported during the immunogenicity follow up period will be summarized by randomized treatment group. The summary will include descriptive statistics and no statistical test will be performed for treatment comparison.

A scatter plot using the antibody percent binding at the last visit in the immunogenicity follow up period as X-axis and the HbA1c value at the same visit as Y-axis will be generated. A similar scatter plot with total daily dose as Y-axis will also be generated.

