- ^u Patients with treatment-emergent insulin lispro antibodies measured at Visit 801 that have not returned to prespecified baseline range (Visit 2), will be asked to undergo additional antibody monitoring as described in [Appendix 8](#). This follow-up assessment also applies to any patient who discontinues study insulin treatment prior to the end of the planned treatment period who has a treatment-emergent antibody response that has not returned to baseline range by Visit 801. It is recommended that the first insulin lispro antibody follow-up visit (Visit 802) be scheduled for all study patients, regardless of treatment-emergent antibody status.
- ^v Health outcomes questionnaires will be administered at the study sites based on the availability of appropriate translations. The questionnaires should be administered prior to other study procedures except at Visit 8 and Visit 18 when questionnaires may be administered following the start of the MMTT.

3. Introduction

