Appendix 7. Classification of Contraceptive Methods

Women of childbearing potential must use either 1 highly effective method of contraception or a combination of 2 effective methods of contraception. The patient may choose to use a double-barrier method of contraception (see chart below).

- Barrier protection methods without concomitant use of a spermicide are not an effective or acceptable method of contraception. Thus, each barrier method must include use of a spermicide (that is, condom with spermicide, diaphragm with spermicide, female condom with spermicide). It should be noted, however, that the use of male and female condoms as a double-barrier method is not considered acceptable due to the high failure rate when these barrier methods are combined.

Methods of Contraception

Highly Effective Methods of Contraception	Effective Methods of Contraception (must use combination of 2 methods)

 • Combined oral contraceptive pill and mini-pill • NuvaRing® • Implantable contraceptives • Injectable contraceptives (such as Depo-Provera®) • Intrauterine device (such as Mirena® and ParaGard®) • Contraceptive patch – ONLY women <198 lb or 90 kg • Total abstinence • Vasectomy 	
 • Male condom with spermicide • Female condom with spermicide • Diaphragm with spermicide • Cervical sponge • Cervical cap with spermicide

**Appendix 8. Insulin Lispro Antibody Follow-Up
Assessment**

Rationale for Insulin Lispro Antibody Follow Up Assessment

As requested by the US FDA, any patient who develops a treatment-emergent anti-insulin lispro antibody (TEADA) response at any time during the study that has not returned to baseline by the completion of Visit 801 should undergo follow-up for antibodies to insulin lispro. Specific thresholds for determining treatment-emergent and return-to-baseline will be specified and documented in the SAP after being agreed with the FDA. Data collected during the insulin lispro antibody follow-up period is intended to evaluate whether antibodies to insulin lispro return to the prespecified baseline range and, in cases where antibodies remain elevated, to assess the possibility of loss of efficacy that may result from insulin neutralizing antibodies.

Eligibility for Insulin Lispro Antibody Follow-Up Assessment

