Any patient who develops a TEADA response that has not returned to the prespecified baseline range (based on Visit 2 sample) by the 4-week safety follow-up visit (based on Visit 801 sample) will undergo additional insulin lispro antibody monitoring. Study visits will continue at approximately 3-month intervals for a maximum of 6 months (approximately 26 weeks) after Visit 801 or until insulin lispro antibodies return to baseline range, whichever occurs sooner.

This follow-up assessment also includes any randomized patient who discontinues study insulin treatment prior to the end of the planned treatment period and has a TEADA response that has not returned to baseline range by Visit 801.

At Visit 801, it is recommended that the first insulin lispro antibody follow-up visit (Visit 802) be scheduled for all study patients, regardless of TEADA status. Visit 802 should occur approximately 13 weeks after Visit 801. Insulin lispro antibody percent binding results will not be provided to sites. When insulin antibody results are available, to determine whether the patient's insulin antibody levels have returned to baseline range, investigators will be notified and Visit 802 can be confirmed or cancelled as appropriate.

During the insulin lispro antibody follow-up period, investigators will be notified if insulin lispro antibodies for a given patient have returned to baseline range, at which time the patient's participation in the follow-up period should be stopped. In the exceptional circumstance that insulin antibody results are not available prior to the next scheduled follow-up visit, patients should be instructed to complete the visit as scheduled; however, the blood sample collected as part of the visit will only be analyzed if the insulin antibody results from the previous visit are still above baseline.

In any case, even where insulin antibodies persist, the insulin lispro antibody follow-up assessment is expected to last no longer than 30 weeks from the protocol-scheduled last treatment visit.

Patients should not participate in other clinical trials during the follow-up period. Patients entering the protocol as part of a maximized extended enrollment addendum (I8B-MC-ITRM[2]) will not be included in the insulin lispro antibody follow-up assessment.

Procedures for Insulin Lispro Antibody Follow-Up Assessment

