5.1. Summary of Study Design

Study ITRM is a Phase 3, prospective, randomized, double-blind, outpatient, multinational, multicenter 3-treatment group, parallel, active-controlled study in patients with type 1 diabetes mellitus (T1D) currently using a multiple daily injections regimen. For patients in the 2 double-blind treatment groups, the study includes a 1-week screening period and an 8-week lead-in period followed by a 52-week treatment period and a 4-week safety follow-up period. For patients in the open-label treatment group who are not in Japan, the treatment period will end after 26 weeks, which will be followed by a 4-week safety follow-up period. Open-label treatment group patients in Japan will follow the same schedule as the double-blind treatment groups. [Figure 5.1](#) illustrates the study design.

[figure not shown]
All patients who complete the 4-week safety follow-up visit (Visit 801) and have treatment-emergent anti-insulin lispro antibodies response that have not returned to the pre-specified baseline range (Visit 2) will be asked to participate in follow-up to monitor insulin lispro antibody levels for up to 26 weeks after Visit 801. The follow-up consists of Visits 802 and 803.

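### The SAP's return-to-baseline analysis set requires the antibody response to arise during the treatment period, so treatment completers first positive at Visit 801 are followed under the protocol but left out of the return-to-baseline percentage

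*SAP*

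**What the plan says.** SAP 6.12.7.2 opens with the entry rule for antibody follow-up: "Any patient who develops a TEADA response at any time during the treatment period (0 to 52 weeks for double-blind treatment groups", continuing "and 0 to 26 weeks for open-label treatment group) that has not returned to baseline at Visit 801". It then turns this rule into an analysis set: "The analyses for return to baseline will only include patients meeting this antibody follow-up entry criteria". The main output for that set is the number and percentage of patients meeting the return-to-baseline criteria at Visits 802 and 803.

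The protocol states entry differently in three places:

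- **Appendix 8, rationale.** Follow-up applies to "any patient who develops a treatment-emergent anti-insulin lispro antibody (TEADA) response at any time during the study that has not returned to baseline" by the time Visit 801 is completed.
- **Appendix 8, eligibility.** "Any patient who develops a TEADA response that has not returned to the prespecified baseline range (based on Visit 2 sample"), judged on the Visit 801 sample. Nothing is said about when the response arose.
- **Section 2, Schedule of Activities, footnote u.** "Patients with treatment-emergent insulin lispro antibodies measured at Visit 801 that have not returned to prespecified baseline range (Visit 2") are asked to undergo further monitoring.

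SAP 5.1 and the introduction to SAP 6.12.7 also describe entry without any window for onset. On Japan, SAP 5.1 adds: "Open-label treatment group patients in Japan will follow the same schedule as the double-blind treatment groups".

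**The concern.** The protocol asks whether the patient has a TEADA response that is unresolved at Visit 801. SAP 6.12.7.2 adds a second condition, that the response arose during treatment. A patient who meets the first condition but not the second gives samples at Visits 802 and 803 that the return-to-baseline analysis does not count.

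Protocol Appendix 8 says the FDA requested this follow-up, and that its purpose is to see whether antibodies return to the baseline range. The analysis set should therefore be the set of patients the protocol sends into follow-up. A narrower set, defined by a clause that contradicts the protocol and other parts of the SAP, would be hard to explain in the study report.

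**Working it through.** The documents give no figure to reproduce. The check compares the two entry rules and places Visit 801 on the study calendar.

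**Step 1: timing of Visit 801** (Protocol 5.3.1 and Section 2)

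- Double-blind completers: Visit 22 (Week 52) + 4 weeks = Week 56.
- Open-label completers outside Japan: Visit 18 (Week 26) + 4 weeks = Week 30.

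The SAP windows end at Week 52 and Week 26. Since 56 > 52 and 30 > 26, Visit 801 lies outside both. An antibody sample is scheduled at Visit 801, so a first positive result there is possible.

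**Step 2: can the treatment period be read to include Visit 801?** No. SAP 6.1 lists the 26-week and 52-week treatment periods separately from the periods that add the safety follow-up visit. SAP 6.12.7.1 likewise summarizes TEADA once for Weeks 0 to 26 and again for Visit 2 to Visit 801. SAP 6.12.7.2 writes out the week ranges. Table 6.2 does list antibody observations through Visit 801, but that defines which observations are postbaseline and does not alter the written window.

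**Step 3: did the protocol leave the window to the SAP?** No. Appendix 8 defers to the SAP only the thresholds for treatment emergence and for return to baseline.

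**Step 4: follow one patient through.** Take a treatment completer first TEADA-positive at Visit 801.

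| Rule | Result |
|---|---|
| Protocol Appendix 8 and footnote u: enters follow-up | Yes |
| SAP 5.1 and SAP 6.12.7: enters follow-up | Yes |
| SAP 6.12.7.1: TEADA-positive, Visit 2 to Visit 801 | Counted |
| SAP 6.12.7.2: meets the entry rule | No |
| SAP 6.12.7.2: return-to-baseline percentage, Visits 802 and 803 | Not counted |

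**Step 5: Japanese open-label patients.** They are treated to Week 52, but SAP 6.12.7.2 gives 0 to 26 weeks for the whole open-label group. A response first seen at their Week 52 sample arises on treatment and still falls outside the stated window. Three provisions narrow this point:

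- SAP 6.4 keeps Japanese patients out of open-label Visit 801 analyses at the primary lock.
- SAP Appendix 2 includes the LY900014+20 arm in the Japan 52-week analyses, with methods similar to the main study.
- Protocol Appendix 8 keeps extended-enrollment patients out of antibody follow-up altogether, so only the global cohort is concerned.

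**Step 6: early discontinuers.** For patients who leave the study early, Visit 801 can fall before Week 52 or Week 26, and the SAP wording does not settle their status. The gap is clear only for completers.

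**The case against.** The best defense is that the sentence in SAP 6.12.7.2 loosely paraphrases the protocol and was never meant to exclude anyone. SAP 5.1 and SAP 6.12.7 state entry in the protocol's terms, and the return-to-baseline output is descriptive with no treatment comparison. The listed immunogenicity objective is TEADA incidence, which SAP 6.12.7.1 covers through Visit 801. Late responders also remain visible in the by-visit antibody listing. All of this is fair and limits the importance of the point. It does not remove it, because the SAP goes on to make that sentence the definition of the analysis set.

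Four stronger readings are tempting, and the documents do not support them:

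- **The HbA1c and insulin dose summaries also lose these patients.** Those summaries are defined by participation in the follow-up, and the scatter plots by the last follow-up visit. Neither has an onset window, so these patients need not be omitted.
- **The TEADA counts in 6.12.7.1 and 6.12.7.2 should share a denominator.** They describe different sets by design, and no planned statistic divides one by the other.
- **Persistence is understated.** Late responders might resolve later than others, or they might be marginal positives that resolve quickly. All entrants are assessed at about 13 and 26 weeks after Visit 801, and the documents contain no resolution data.
- **The omitted share can be estimated from the calendar.** If onset were uniform from Week 0, the share first seen in the last 4 weeks would be 4/56 = 7.1% (double-blind) or 4/30 = 13.3% (open-label outside Japan). Counting from Visit 2 at Week -8 gives 4/64 = 6.3% or 4/38 = 10.5%. The documents support neither uniform onset nor equal emergence after study insulin stops.

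**Conclusion.** The analysis-set rule in SAP 6.12.7.2 is wrong as written. It contradicts Protocol Appendix 8, footnote u of the Schedule of Activities, and the SAP's own sections 5.1 and 6.12.7. The clear consequence is that treatment completers first TEADA-positive at Visit 801 are followed but not counted in the return-to-baseline number and percentage. The 26-week limit is also a poor fit for global-cohort Japanese open-label patients, though SAP Appendix 2 may deal with them.

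The effect is confined to one descriptive safety summary. It has no bearing on type I error, power or the primary analysis. The documents give no rate of TEADA onset or resolution, so the number of patients affected and the direction of any bias are unknown. The conclusion rests on reading the sentence literally; if the intention was to match the protocol, the text needs to say so.

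**What to change.** Reword the entry rule in SAP 6.12.7.2 to cover *a TEADA response at any visit after Visit 2, up to and including Visit 801, that is still outside the baseline range on the Visit 801 sample*. State that this applies to all arms, including Japanese open-label patients of the global cohort through their own Visit 801. Use that one set for the return-to-baseline analyses.

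This also settles the status of early discontinuers, because it depends on the Visit 801 sample and not on calendar weeks. The cost is one sentence in the SAP and the matching change to the derivation of the analysis set. No visits or samples are added, since the protocol already schedules them.
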